5.10 Other variables

Not applicable.

STATISTICAL ANALYSIS PLAN Protocol No: MEIN/14/FEB-PWV/001 (FORWARD)		

Version Number: 2.0 Date of Issue: 2018-03-16	Page 21 of 22	

	Version Number: 2.0 Date of Issue: 2018-03-16	Page 21 of 22
Version Number: 2.0 Date of Issue: 2018-03-16	Page 21 of 22	

5.11 Interim analyses

Not applicable.

6 QUALITY CONTROL

The responsible Project Manager will review the SAP before it is provided to the Sponsor for review. The SAP will be signed off only when approval from the Sponsor's representative is received.

Log files of all SAS® programs needed for analysis will be checked for errors, warnings and suspicious notes by the statistical programmer. All findings will be either eliminated or commented upon. The final version of each program will be stored along with its log file in the electronic archive.

All programs will be validated by the author.

The agreement of the program outputs with the SAP, their consistency and plausibility will be checked by the TS. Moreover, the TS will review the outputs regarding completeness, readability and comprehensibility.

8 APPENDICES

8.1 Formulas for derived variables

Variable	Description
Durations between two dates	Later date minus earlier date plus 1, expressed in days. (Remark: Duration will be 1, if both dates are the same.)
Subject compliance (%)	Number of tablets actually taken x 100 / expected number of tablets which should have been taken.
Number of tablets actually taken	Difference between the number of tablets handed out to the patient and the number of unused tablets returned or declared lost by the patient
Expected number of tablets per visit	Number of days of date of visit x – date of visit x-1
Total expected number of tablets taken	(Sum of number of all days of date visit x – date visit x-1) + 1
Compliant per visit	Compliance \geq 60% and no more than 120% of the required study drug intake since the last visit

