2.3 Study design

This study is designed as a randomized, active-controlled, open label, evaluator blind, parallel group, multi-center, multi-national, Phase IV trial. Patients will be randomized 1:1 to receive febuxostat or allopurinol.

There will be approx. 35 sites in the following countries: Germany, the Netherlands, Italy, Poland, Serbia, Romania.

Study duration for individual patients will be 39 weeks. This includes a one-week run-in/screening period which can be extended to max 30 days in case of re-testing, followed by a 36 weeks treatment and a 2 weeks safety follow-up (by phone call).

The study physician responsible for randomization and drug supply handling is unblinded to study medications and therefore will not be involved in the main efficacy evaluations of each patient randomized in the study.

Conversely, the study physician/s responsible for the main efficacy evaluation (Pulse Wave Velocity) will be blind to study treatments. In addition, key efficacy variables will be performed by an independent core laboratory where the central reader will be blind to the treatment assigned to patients.

Fasting lipid levels, NTproBNP, BNP, markers of inflammation and endothelial activation/adhesion, oxidative stress parameters, eGFR, changes in urine albumin excretion as evaluated by first morning albumin/creatinine ratio will be also measured by a central laboratory.

Eligible patients will be randomized to treatment with allopurinol 100 mg or febuxostat 80 mg (1:1 ratio). Up-titration of allopurinol or febuxostat to the maximum dose permitted in the study may be performed between Week 2 and Week 10, see flow chart below for details.

A follow-up safety assessment will be performed by a phone call 2 weeks after study termination.

STATISTICAL ANALYSIS PLAN

[figure not shown]
Protocol No: MEIN/14/FEB-PWV/001 (FORWARD)

Version Number: 2.0

Date of Issue: 2018-03-16

Page 10 of 22

Trial flow chart

Notes:

	Day -30 to Week -1	Day 0	Week 2 ± 4 days	Week 12 ± 4 days	Week 24 ± 4 days	Week 36 ± 4 days	Week 38 + 3 days after
	Visit -1	Visit 0	Visit 1	Visit 2	Visit 3	Visit 4	Visit 5 Phone call
	Screening	Randomization	On Treatment Visit	On Treatment Visit	On Treatment Visit	End of Study visit	Safety Follow up
Inclusion/exclusion crit.	X						
Informed consent	X						
Randomization		X					
Medical history	X						
Concomitant medications	X	X	X	X	X	X	
Physical examination	X			X	X	X	
Vital signs (BP, HR body temperature)	X	X		X	X	X	

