3.3 Individual protocol deviations

Any deviation from protocol will be discussed case by case before database lock or unblinding whether the deviation has to be regarded as minor or as major (and therefore lead to exclusion from particular analysis populations).

The assessment of individual protocol deviations will be made in a Data Review Meeting. A complete listing of protocol deviations and the judgment for assessment of subject disposition will be signed before database lock. All deviations along with the disposition of each subject will be recorded in a separate database member that will become part of the study database. A description of all major protocol violations will be included in the table part of the CSR.

Criteria for major protocol violations will at least include:

- Any substantial violation of in- or exclusion criteria.
- Use of prohibited concomitant medication that may interfere with the assessment of efficacy.
- Receipt of wrong dose of study medication. Randomization errors.
- Trial subjects that developed study withdrawal criteria but were not withdrawn, receipt of wrong dose, use of concomitant medications not allowed
- Non-compliance regarding intake of study drug, i.e. less than 60% or more than 120% of required study drug intake since last visit (see also section 5.3)

STATISTICAL ANALYSIS PLAN Protocol No: MEIN/14/FEB-PWV/001 (FORWARD)	
Version Number: 2.0 Date of Issue: 2018-03-16	Page 13 of 22

Version Number: 2.0	Page 13 of 22
Date of Issue: 2018-03-16	

Any deviation from the protocol (to be classified as major or minor) will be accepted only in case of emergency and/or after a written agreement with the Sponsor.

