5.3 IMP exposure, compliance

Treatment compliance will be monitored from Visit -1 to Visit 4 (end of study treatment).

The amount of study medication taken by the subject will be derived by counting the number of tablets dispensed and returned in the blister which will be recorded in the eCRF.

The patient compliance for the study treatment period is calculated as described in section 8.1.

A patient who has taken at least 60% and no more than 120% of the required study drug intake since the last visit will be considered compliant.

All IMP treatment details will be listed.

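### The SAP's compliance formula assumes one tablet a day for every patient although doses may be up-titrated; if titration adds tablets, the 60-120% limits misclassify patients in both directions.

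*SAP*

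**What the plan says.** Section 8.1 defines compliance as "Number of tablets actually taken x 100 / expected number of tablets which should have been taken". The numerator is a tablet count, not milligrams: "Difference between the number of tablets handed out to the patient and the number of unused tablets returned or declared lost by the patient". The denominator for each visit is "Number of days of date of visit x – date of visit x-1", and for the whole study it is "Sum of number of all days of date visit x – date visit x-1) + 1". Neither denominator has a term for dose, arm or tablets per day.

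Section 2.3 starts patients on allopurinol 100 mg or febuxostat 80 mg and then states: "Up-titration of allopurinol or febuxostat to the maximum dose permitted in the study may be performed between Week 2 and Week 10". The visit table in 2.3 shows IMP dispensing at Day 0 and Weeks 2, 12 and 24.

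Section 3.3 lists among the minimum criteria for a major violation an intake of "less than 60% or more than 120% of required study drug intake since last visit". Section 5.3 gives the same limits from the other side: "A patient who has taken at least 60% and no more than 120% of the required study drug intake since the last visit will be" classed as compliant. It also says "Treatment compliance will be monitored from Visit -1 to Visit 4 (end of study treatment").

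PP1 (section 4.3) requires completion without any major violation. PP2 removes only major violations that might affect evaluation of the primary objective. Section 5.7 makes the FAS primary and PP2 the sensitivity population.

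**The concern.** The limits in 3.3 and 5.3 refer to required intake, which depends on what was prescribed. The formula in 8.1 replaces this with calendar days. The two agree only at one tablet a day, a condition that the SAP never states, in a trial where the dose may change after Week 2.

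If a higher dose means more tablets, the ratio fails in both directions. Adherent titrated patients look like over-users and meet a major-violation criterion, while patients who take a fraction of their tablets look compliant. The errors would follow dose. They would also follow treatment arm if the two drugs need different tablet counts. A per-protocol set built on such a ratio would select patients by treatment and dose, which defeats its purpose as a robustness check.

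**Working it through.** **Inputs.** The nominal visit intervals come from the visit table in 2.3: Day 0 to Week 2 = 14 days, Weeks 2-12 = 70, Weeks 12-24 = 84, Weeks 24-36 = 84, total 252. The limits of 60% and 120% come from 3.3 and 5.3. Tablets per day after titration, k, is not in the SAP; k = 1 to 3 is an assumed range.

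**Formula.** Compliance % = 100 × tablets taken / days in the interval. The SAP states no compliance result to reproduce.

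**Full interval, full adherence.** Tablets taken = k × days, so the score is 100 × k %.
- k = 1: 100% in every interval, no error.
- k = 2: 200%.
- k = 3: 300%.

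**Weeks 2-12, when titration falls inside the interval.** With d days at k tablets and 70 − d days at one, the score is 100 × (70 − d + k·d) / 70.

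| Titrated at week | d | k = 2 | k = 3 |
|---|---|---|---|
| 2 | 70 | 200% | 300% |
| 4 | 56 | 180% | 260% |
| 6 | 42 | 160% | 220% |
| 8 | 28 | 140% | 180% |
| 10 | 14 | 120% | 140% |

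At k = 2 the limit is passed when (70 + d)/70 > 1.2, that is, when d > 14 days. Titration at Week 10 gives exactly 120% and still passes in that interval, but the next two intervals give 200%.

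**Whole study, full adherence**, with the 8.1 denominator 252 + 1 = 253.
- k = 2 from Week 2: (14 + 2×70 + 2×168)/253 = 490/253 = 193.7%. From Week 10: (14 + 56 + 2×14 + 2×168)/253 = 434/253 = 171.5%.
- k = 3 from Week 2: 728/253 = 287.7%. From Week 10: 616/253 = 243.5%.

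**Opposite error.** Over a full interval at k tablets a day, a patient whose true adherence is a % scores k × a. The patient passes when 60 ≤ k × a ≤ 120, so a lies between 60/k and 120/k.
- k = 2: true adherence of 30-60% passes.
- k = 3: true adherence of 20-40% passes.

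**Check of the remedy.** If the denominator is the sum of prescribed tablets over the days, full adherence scores 100% for any k, and the 60-120% limits apply to true adherence.

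**Start visit in 5.3.** Adding the screening period to the 253-day total would lower an adherent patient's overall score by 7/260 = 2.7% for a 7-day screening or 30/283 = 10.6% for the 30-day maximum. Even the latter leaves 253/283 = 89.4%, well inside the limits.

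**The case against.** The central fact is absent. The SAP gives no tablet strength, daily tablet count or maximum dose; those details commonly sit in the protocol, which was not available for this point. One tablet of higher strength at each step fits the text equally well, and the formula is then right. This stands, and it makes the point conditional.

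A reader might infer from the dispensing schedule that dose steps between Weeks 2 and 12 come from the Week 2 stock, and hence that titration means more tablets. The table lists scheduled visits only and does not say how titration is supplied. The inference is compatible with the text but not shown by it.

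Exclusion is also not automatic. Section 3.3 has deviations discussed case by case before lock, and PP2 drops only violations bearing on the primary objective. Scores of 200-300% would be conspicuous there. This stands in part: the meeting could set aside the high values, but an under-taker who scores within the limits gives it nothing to notice.

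A reader might also take the Visit -1 start in 5.3 to mean that untreated screening days enter the denominator. The same section confines the calculation to the treatment period, and dispensing begins at Visit 0. The violation criterion works per visit interval, so the overall total does not drive it. This is loose wording, not a second defect.

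**Conclusion.** The point holds in conditional form. As written, 8.1 is correct only if every dose in both arms is one tablet a day, and the SAP does not state this. If titration leads to 2 or 3 tablets a day, a fully adherent patient scores 200-300% over a full interval, and patients at 30-60% or 20-40% of prescribed intake pass. PP1 would be affected, as would the PP2 sensitivity analysis to the extent that the data review meeting acts on the ratio.

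Two stronger readings are not supported. The SAP does not show that titrated patients in this trial will be false violators, because it does not show that any patient takes several tablets a day. A distortion that differs by arm needs a further assumption, unequal tablet counts between the drugs. The primary result is not at risk: the FAS has no compliance criterion.

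**What to change.** In 8.1, define expected tablets, per interval and in total, as the sum over days of the prescribed tablets per day recorded for that day, counted from first IMP intake. Apply the 60-120% limits in 3.3 and 5.3 to that ratio. Using one definition for both levels also removes the present mismatch in which only the total adds a day (253 against 252, about 0.4%). As a minor wording correction, start compliance in 5.3 at Visit 0, where dispensing begins.

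If every dose is in fact one tablet a day, the classification is essentially unchanged and the new wording simply makes the assumption explicit. The cost is a text change and one derived variable. No new data are needed, provided the prescribed daily tablets are recorded in the eCRF; this should be confirmed before the data review meeting.

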8.2 List of Tables, Listings, Figures

A complete lists of tables, listings figures (TLFs) will be given in a separate document which can be updated without updating the SAP. The list will serve as a reference for both the Sponsor, the trial statistician and the statistical programmer and includes the totality of statistical output to be produced. Therefore, this list will be approved by both parties before commencing the statistical programming.

All output will be headed with an appropriate heading specifying the study ID and abbreviated study title.

All output will be dated and have page numbers in the form 'Page [x / y]' where x denotes the current page within an output and y the total number of pages of that output.

All statistical output will identify the underlying analysis populations and indicate the number of patients / events in this population (N) and the number of patient/events actually contributing to the particular output (n). All statistical output will be presented per treatment group and in total (if applicable).

All patient listings will contain additionally to the patient identification the analysis population and the treatment group.
